### 6.3 Follow-up Period

The safety follow-up visit will occur at least 2 weeks after the last dose (+ 7 days). During this visit, the following procedures and assessments must be performed:

- Review adverse events and concomitant medications.
- Measure vital signs (sitting blood pressure, pulse, breathing, and temperature) and weight.

#### **6.4 Other Information for Study Visits**

Unscheduled visits and/or procedures may be required in addition to the visits and procedures detailed above. The additional visits or procedures are at the discretion of the investigator. The details of these unscheduled visits or procedures will be recorded in the source documents and entered into the eCRFs.

If a subject misses a scheduled visit, the clinical site is to make every effort to have the subject visit the site as soon as possible. If a subject may delay 7 or more days from the scheduled date, the site should contact the Sponsor for the discussion of how to determine.

#### **6.5 Data Quality**

Monitoring and auditing procedures defined/agreed by the Sponsor will be followed in compliance with current GCP guidelines. Each clinical site will be visited at regular intervals (about 6 weeks) by a monitor to ensure compliance with the study protocol, GCP guideline, and other regulatory aspects. This will include on-site review of the source documents and eCRFs for the completeness and clarity, consistency between source documents and eCRFs, and clarification of administrative matters.

#### **6.6 Documentation**

Entries made in the eCRF must be either verifiable against source documents or have been directly entered into the eCRF, in which case the entry in the CRF will be considered as the source data. The source data parameter to be verified and the identification of the source document must be documented. The study file and all source data should be retained/archived until notification by the Sponsor for change of archive site or destruction.

## **7. Ethical and Legal Aspects**

### **7.1 Institutional Review Board (IRB)**

Documented approval from the IRB will be obtained for all participating clinical site(s) prior to study start, according to GCP and applicable laws and regulations. When necessary, an extension, amendment, or renewal of the IRB approval must be obtained and also forwarded to the Sponsor. The IRB must supply to the Sponsor, upon request, a list of the IRB members involved in the vote and a statement to confirm that the IRB is organized and operates according to GCP and applicable laws and regulations.

### **7.2 Ethical Conduct of the Study**

The procedures set out in this protocol, pertaining to the conduct, evaluation, and documentation of this study, are designed to ensure that the Sponsor and investigator abide by GCP guidelines and under the guiding principles detailed in the Declaration of Helsinki. The study will also be carried out in keeping with applicable local laws and regulations. This may include an inspection by the Sponsor representatives and/or Regulatory Authority representatives at any time. The investigator must agree to the inspection of study-related records by the Regulatory Authority/Sponsor representatives, and must allow direct access to source documents to the Regulatory Authority/Sponsor representatives.

Modifications to the study protocol will be implemented by the investigator only after the Sponsor's approval. However, the investigator may implement a deviation form, or change of the protocol to eliminate any immediate hazard(s) to the trial subjects without prior IRB/Sponsor approval. The implemented deviation or change, the reasons for it and, if appropriate, the proposed amendment should be submitted to the IRB/Sponsor as soon as possible. Any deviations from the protocol must be fully explained and documented by the investigator.

### **7.3 Regulatory Authority Approvals/Authorizations**

Regulatory Authority approvals/authorizations/notifications, where required, will be in place and fully documented prior to the study's start.

### **7.4 Subject Information Consent**

A core information and Informed Consent Form will be provided. Prior to the beginning of the study, the investigator must have the IRB written approval of the Informed Consent Form and any other written information that will be provided to the subjects. The written approval of the IRB with the approved Informed Consent Form must be in the study files.

Written informed consent must be obtained before any study specific procedure takes place. Participation in the study and date of informed consent given by the subject should be documented appropriately in the subject's files.

### **7.5 Insurance**

All subjects participating in the study will have insurance coverage by the Sponsor, which is in line with applicable laws and/or regulations.

### **7.6 Confidentiality**

All records identifying the subject will be kept confidential and, to the extent permitted by the applicable laws and/or regulations, will not be made publicly available.

Subject names will not be supplied to the Sponsor. Only the subject number and subject initials will be recorded in the eCRF, and if the subject name appears on any other document (e.g. pathologist report), it must be obliterated before a copy of the document is supplied to the Sponsor. Study findings stored on a computer will be stored in accordance with local data protection laws. The subjects will be informed in writing that representatives of the Sponsor, IRB, or Regulatory Authorities may inspect their medical records to verify the information collected, and that all personal information made available for inspection will be handled in strictest confidence and in accordance with local data protection laws.

Even if the results of the study are published, the subject's identity will remain confidential. The investigator will maintain a list to enable subjects' records to be identified.

## **8. Statistical Methods and Determination of Sample Size**

### **8.1 Statistical and Analytical Plan**

#### 8.1.1 Analytical Populations

##### Intent-to-Treat Population

An intent-to-treat (ITT) population will include subjects who have administered at least one dose of study medication and who have baseline and any post-baseline efficacy data. This cohort will be evaluated for all efficacy variables.

##### Per-Protocol Population

All subjects valid for ITT who meet ALL the following criteria will be ‘valid per protocol’ (also called ‘valid for efficacy’):

- Complete at least 2 weeks of treatment after randomization.
- Have both baseline and at least 2 weeks of efficacy data.
- Subject did not have any significant violation after randomization.

Additional criteria may be added prior to unblinding the study database.

As with the ITT population, this per-protocol (PP) cohort will also be evaluated for all efficacy variables.

##### Safety Population

Any subject who administers at least one dose of study medication and has any post-randomization safety data collected will be included in the evaluation of safety.

#### 8.1.2 Treatment Group Comparability

Demographic variables, medical history, treatment duration, and efficacy variables at baseline will be summarized by treatment group for the subjects valid for potential safety analysis. Because, in theory, the goal of randomization is to balance out the patient characteristics, statistical tests are not planned for these variables.

#### 8.1.3 Primary Efficacy Analyses

The change from baseline to Week 12 in HbA1c will be compared for the experimental groups versus the control group using analysis of variance (ANOVA) methods if the change is approximately normally distributed. If the change is markedly non-normally distributed then Wilcoxon rank sum tests will be used. Specifically, all three experimental groups will be compared to the control group on the change: Dose A vs. D, B vs. D, and C vs. D.

The change from baseline to Week 12 in BW will be compared for the experimental groups versus the control group using ANOVA methods if the change is approximately normally distributed. If the change is markedly non-normally distributed then Wilcoxon rank sum tests will be used.

#### 8.1.4 Secondary Efficacy Analyses

The change from baseline to Week 12 in FPG level will be compared for the experimental groups versus the control group using ANOVA methods if the change is approximately normally distributed. If the change is markedly non-normally distributed then Wilcoxon rank sum tests will be used.

The proportion of subjects achieving HbA1c goal of <7.0% at Week 12 will be compared for the experimental groups versus the control group using chi-square testing methods or Fisher's exact tests, as appropriate.

The proportion of subjects achieving HbA1c goal of <6.5% at Week 12 will be compared for the experimental groups versus the control group using chi-square testing methods or Fisher's exact tests, as appropriate.

The change from baseline to Week 12 in waist circumference will be compared for the experimental groups versus the control group using ANOVA methods if the change is approximately normally distributed. If the change is markedly non-normally distributed then Wilcoxon rank sum tests will be used.

The change from baseline to Week 12 in mean value of postprandial (2 hours after dinner) blood glucose level for 2 weeks will be compared for the experimental groups versus the control group using ANOVA methods if the change is approximately normally distributed. If the change is markedly non-normally distributed then Wilcoxon rank sum tests will be used.

The change from baseline to Week 12 in OGTT will be compared for the experimental groups versus the control group using ANOVA methods if the change is approximately normally distributed. If the change is markedly non-normally distributed then Wilcoxon rank sum tests will be used.

The change from baseline to Week 12 in ADDQoL questionnaire scores will be compared for the experimental groups versus the control group using ANOVA methods if the change is approximately normally distributed. If the change is markedly non-normally distributed then Wilcoxon rank sum tests will be used.

#### 8.1.5 Exploratory Efficacy Analyses

The change from baseline to Week 12 in thyroid function test (TSH, T3, T4), serum parameters (insulin, adiponectin, C-peptide, leptin, glucagon), and urine parameters (zinc, glucose, microalbumin, copper) will be compared for the experimental groups versus the control group using ANOVA methods if the change is approximately normally distributed. If the change is markedly non-normally distributed then Wilcoxon rank sum tests will be used.

### 8.1.6 Safety Analyses

Safety variables will be summarized with descriptive statistics, overall and by each of the four groups, separately. The safety variables include: Blood samples, ECG evaluation, physical examination endpoints, vital signs, adverse events (AEs) and episodes of hypoglycemia and hyperglycemia. Continuous safety variables will be summarized with means, standard deviations, medians and ranges. Categorical safety variables will be summarized with counts and percentages.

AEs will be coded using MedDRA (Medical Dictionary for Regulatory Activities). AEs will be summarized by System Organ Class (SOC) and Preferred Term (PT). AEs will also be summarized by relationship to the study drug, seriousness and severity.

A treatment-emergent AE (TEAE) will be defined as an AE that began or worsened on or after the first treatment dose. AEs recorded prior to the first application of study treatment will be considered non-treatment-emergent. AEs with insufficient date or time information to determine whether or not they were treatment-emergent will be considered treatment-emergent.

All reported AEs (treatment-emergent or not) will be listed. Only TEAEs will be summarized.

Statistical tests are not planned for safety variables.

### 8.1.7 CHP Concentration Analyses

Levels of CHP may be assessed in blood for a subset of subjects if there are residual serum and/or plasma after completion of protocol-required tests. No statistical tests are planned for these data.

### 8.1.8 Missing Data

No adjustments for missing data and no imputation methods are planned for this phase 2 study.

### 8.1.9 General Statistical Considerations

Continuous variables will be summarized with means, standard deviations, medians and ranges. Categorical variables will be summarized with counts and percentages. P-values less than or equal to 0.05 will be considered statistically significant. Because this is a phase 2 clinical trial and because it was not formally powered with statistical algorithms, no adjustments for multiple comparisons will be made to the results presented in this study.

## 8.2 Determination of Sample Size

This is a Phase 2 clinical trial to evaluate safety and explore the potential efficacy of the study drug. Therefore, the number of subjects was not based on formal statistical power considerations. In this clinical trial, a total of 64 subjects was deemed sufficient and will be enrolled and randomly assigned to be administered with 1 of 3 dose levels of Cyclo-Z or placebo.

### **8.3 Interim Analyses**

No interim analyses are planned for this Phase 2 study.

## **9. ADVERSE EVENTS**

### **9.1 Warnings / Precautions**

This study medication must be kept out of reach of children. See the Investigator's Brochure for additional information.

### **9.2 Adverse Event Monitoring**

Subjects must be carefully monitored for AEs. AEs should be assessed in terms of their seriousness, severity, and relationship to the study drug.

### **9.3 Adverse Event Definitions**

#### **9.3.1 Adverse Event (AE)**

An AE is any untoward medical occurrence in a clinical trial subject administered with an investigational product under investigation. The AE does not necessarily have to have a causal relationship with this treatment. An AE can therefore be any unfavorable and unintended sign (including an abnormal laboratory finding), symptom, or disease temporally associated with the use of an investigational product, whether or not considered related to the investigational product.

AEs associated with the use of a drug in humans, whether or not considered drug related, include the following:

- An AE occurring in the course of the use of a drug product in professional practice;
- An AE occurring from an overdose whether accidental or intentional;
- An AE occurring from drug abuse;
- An AE occurring from drug withdrawal;
- An AE where there is a reasonable possibility that the event occurred purely as a result of the subject participation in the study (e.g. AE or SAE due to discontinuation of ant-depressants during wash-out phase) must also be reported as an AE, even if it is not related to the investigational product.

The clinical manifestation of any failure of expected pharmacological action is not recorded as an AE, if it is already reflected as a data point captured in the CRF. If, however, the event fulfills any of the criteria for a 'serious' AE, it must be recorded and reported as such.

#### **9.3.2 Serious Adverse Event (SAE)**

An SAE is any untoward medical occurrence that at any dose:

- Results in death;
- Is life-threatening;

- Requires in-patient hospitalization or prolongation of existing hospitalization;
- Results in persistent or significant disability or incapacity;
- Is a congenital anomaly or birth defect;
- Is an important medical event.

**Life-threatening:** The term ‘life-threatening’ in the definition of ‘serious’ refers to an AE in which the subject was at risk of death at the time of the event. It does not refer to an AE that hypothetically might have caused death if it were more severe.

**Hospitalization:** Any AE leading to hospitalization or prolongation of hospitalization will be considered as ‘serious’, UNLESS at least one of the following exceptions are met:

- The admission results in a hospital stay of less than 12 hours OR,
- The admission is pre-planned (i.e., elective or scheduled surgery arranged prior to the start of the study) OR,
- The admission is not associated with an AE (e.g. social hospitalization for purposes of respite care).

However, it should be noted that invasive treatment during any hospitalization may fulfill the criteria of ‘medically important’ and as such may be reportable as a SAE dependent on clinical judgment.

**Disability** means a substantial disruption of a person’s ability to conduct normal life’s functions.

**Important medical event:** Any AE may be considered serious because it may jeopardize the subject and may require intervention to prevent another serious condition. As guidance for determination of important medical events refer to the ‘WHO Adverse Reaction Terminology – Critical Terms List’. These terms either refer to or might be indicative of a serious disease state.

Such reported events warrant special attention because of their possible association with a serious disease state and may lead to more decisive action than reports on other terms.

### 9.3.3 Unexpected Adverse Event

An unexpected AE is any adverse drug event, the specificity or severity of which is not consistent with the info presented in the current Investigator’s Brochure. Also, reports that add significant information on specificity or severity of known, already documented AE constitute unexpected AEs. For example, an AE more specific or more severe than described in the Investigator’s Brochure would be considered ‘unexpected’. Specific examples would be: (a) acute renal failure as a labeled AE with a subsequent new report of interstitial nephritis and (b) hepatitis with a first report of fulminant hepatitis.

### 9.3.4 Relationship of Adverse Event to Investigational Product

The assessment of the relationship of an AE to the administration of study drug is a clinical decision based on all available information at the time of the completion of the CRF.

An assessment of 'No' would include:

- The existence of a clear alternative explanation (e.g., mechanical bleeding at surgical site);
- Non-Plausibility (e.g., the subject is struck by an automobile when there is no indication that the drug caused disorientation that may have caused the event);
- Cancer developing a few days after the first drug administration.

An assessment of 'Yes' indicates that there is a reasonable suspicion that the AE is associated with the use of the investigational drug.

Factors to be considered in assessing the relationship of the AE to study drug include:

- The temporal sequence from drug administration: The event should occur after the drug is given. The length of time from drug exposure to event should be evaluated in the clinical context of the event.
- Recovery on discontinuation (de-challenge), recurrence on reintroduction (re-challenge): Subject's response after drug discontinuation (de-challenge) or subject's response after drug reintroduction (re-challenge) should be considered in the view of the usual clinical course of the event in question.
- Underlying, concomitant, intercurrent diseases: Each report should be evaluated in the context of the natural history and course of the disease being treated and any other disease the subject may have.
- Concomitant medication or treatment: The other drug the subject is taking or the treatment the subject receives should be examined to determine whether any of them may be suspected to cause the event in question.
- The pharmacology and pharmacokinetics of the test drug: The pharmacokinetic properties (absorption, distribution, metabolism, and excretion) of the test drug, coupled with the individual subject's pharmacodynamics should be considered.

### 9.3.5 Severity of Adverse Event

The severity of AEs should be graded as follows:

Mild – Usually transient in nature and generally not interfering with normal activities

Moderate – Sufficiently discomforting to interfere with normal activities

Severe – Prevents normal activities

### 9.3.6 Adverse Event Documentation

All AEs occurring after the subject has signed the informed consent must be fully recorded in the subject's CRF.

Documentation must be supported by an entry in the subject's file. A laboratory test abnormality considered clinically relevant, e.g., causing the subject to withdraw from the study, requiring treatment or causing apparent clinical manifestations, or judged relevant by the investigator, should be reported as an AE. Each event should be described in detail along with start and stop dates, severity, relationship to investigational product, action taken, and outcome.

#### **9.4 Reporting of Serious Adverse Events/Pregnancy**

SAEs, including laboratory test abnormalities fulfilling the definition of serious, after signing the informed consent, and during follow-up period must immediately (within 24 hours of the investigator's awareness) be reported to the person/parties as detailed in the study file. A SAE form must also be completed within 24 hours of the investigator's awareness and forwarded to the designated person/parties as detailed in the study file. Each SAE must be followed up until resolution or stabilization by submission of updated reports to the designated person/parties.

When required, and according to local law and regulations, SAEs must be reported to the IRB and Regulatory Authorities.

Pregnancy occurring during a clinical investigation, although not considered a SAE, must be reported to the Sponsor within the same timelines as a SAE on Pregnancy Monitoring Form. The outcome of the mother or the child should be reported. This also applies to pregnancies following the administration of the investigational product to the father prior to sexual intercourse.

#### **9.5 Procedures for Managing Hypoglycemia and Hyperglycemia**

Subjects will continue to be on their usual diabetes medications including insulin, sulfonylurea, metformin and/or glitathiazone derivatives. If a subject develops hypoglycemia during the study period per definitions stated in Appendix 4, the doses of antidiabetic agents will be adjusted to maintain glycemic control levels (fasting plasma glucose between 70-130 mg/dl). The standard of care mandated by the American Diabetes Association and optimal healthcare for all participants while meeting the study needs will be followed by the Investigator. Specifically, subjects will monitor and record their daily glucose levels twice daily (before breakfast and 2 hours after dinner) and be seen by the Investigator at each visit.

If during this time a subject experiences hypoglycemia more than twice, he/she must consult with the Investigator. Reasons for hypoglycemia will be sought such as changes in dietary or exercise patterns. If there is no apparent reason for hypoglycemia, then a subject on insulin will be instructed to reduce his/her insulin dose by 4 units or 10% of his/her usual insulin dose, observe the effects of the dose reduction for 3 days, and then report to the Investigator. If the subject continues to develop hypoglycemia, the dose of insulin will be reduced by another 2-4 units. Similarly, if the subject is on an oral hypoglycemic agent they will be instructed to reduce the dose of their oral hypoglycemic agent in a stepwise fashion. This life style modification is mandatory in the study protocol although the Investigator cannot monitor the individual's compliance to the instruction. Subjects who experience symptomatic hypoglycemia will be instructed to ingest a rapidly absorbed sugar. The most convenient fast-acting sugar is found in glucose tablets or gels and will be provided to subjects. These interventions will be subject-specific and must be undertaken under the direction of the Investigator and/or their own health provider to prevent and solve unforeseen hypoglycemic problems.

If a subject experiences serious hypoglycemia on a frequent basis, the Investigator may direct the subject to discontinue the use of all anti-diabetic drug intake and insulin injections and may also discontinue the use of the study drug until the cause of the hypoglycemia is determined. The subject will be instructed to continue to follow the protocol for record keeping, blood analysis and others.

If a subject experiences an increase in FPG level of >270 mg/dl from baseline to Week 6 or >240 mg/dl from Week 6 to 12, the subject will be instructed to take his/her own hypoglycemic agent. It is expected that glucose levels can be controlled in most diabetic subjects by these treatments. If the subject's blood glucose levels do not decrease to an acceptable level (<240 mg/dl) after 2 weeks, the subject will be referred to a diabetologist and will be terminated from the study. The study physician will continue to evaluate and treat the subject as needed until healthcare is turned over to the diabetologist.

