## **5.8 Subject Education on Hypoglycemia/Hyperglycemia and its Management**

All subjects will be instructed in life style modification and asked to maintain a stable diet and daily exercise routine and to keep a daily record of their blood glucose level before breakfast and 2 hours after dinner. Hypo- or hyperglycemia are of particular concern and if either occurs, it will be handled in a standard fashion as outlined in Section 9.5, Procedures for Managing Hypoglycemia and Hyperglycemia.

Although Cyclo-Z treatment alone does not cause hypoglycemia in human as demonstrated in the prior informal study, it may potentially lead to hypoglycemia when interacting with other anti-diabetic drugs. The interaction between Cyclo-Z and other oral anti-diabetic agents or obesity medications are not known at this time. However, some anti-diabetic agents such as insulin injection, sulfonyl derivatives or other insulin secretion stimulating agents may cause hypoglycemia regardless of Cyclo-Z treatment. Improved insulin resistance during the study requires reduction in the use of other insulin and insulin secretagogues. Thus, subjects' blood glucose levels should be closely monitored to detect hypoglycemia in order for the use of other anti-diabetic agents to be appropriately reduced. For the purpose of record keeping and maintaining subject's health, all subjects will be provided with their own glucometer to measure their blood glucose levels. If there are subjects with a possibility of developing acute hypoglycemia while using their current hypoglycemic agents concomitantly with Cyclo-Z, they will be instructed to carry commercial glucose tablets with them to take when feeling dizzy and weak. While taking Cyclo-Z, an improvement in insulin sensitivity or symptoms of hypoglycemia will not develop acutely. Furthermore, 2-week periodical examinations and subjects' daily blood glucose measurements will keep their glucose levels on track and help prevent them from experiencing possible hypoglycemic episodes.

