## **5.9 Medication Accountability and Treatment Compliance**

Subjects will return all unused study medications with the diary at Visits 3, 4, 5, 6, 7, and 8 (Weeks 2, 4, 6, 8, 10, and 12) or at Early Termination Visit. The returned medications and diaries will be reviewed with the subject to evaluate the medication accountability and treatment compliance. If a subject misses 3 or more doses out of total 2-week doses (i.e., 14 doses), the site should contact the Sponsor for the discussion of potential early termination.

All study medication supplies should be accounted for at the termination of the study and a written explanation provided for discrepancies. All unused study medication supplies and packaging materials are

to be inventoried and returned to the Sponsor by the investigator. The investigator is not permitted to return or destroy unused clinical drug supplies or packaging materials unless authorized by the Sponsor.

The medication doses for the diabetes treatment should not be changed during the 3-month treatment period.

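### Section 5.9 bars diabetes dose changes without excepting the reductions that 5.8 and 9.5 call for, and 9.5 states no route or time for reporting a single severe hypoglycaemic event

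*Protocol*

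**What the plan says.** Three sections of the Protocol bear on background diabetes doses.

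- Section 5.9, last sentence: "The medication doses for the diabetes treatment should not be changed during the 3-month treatment period". It has no exception and no pointer to another section.
- Section 5.8: "Improved insulin resistance during the study requires reduction in the use of other insulin and insulin secretagogues". It asks for close glucose monitoring so that other agents can be cut back. Of hypo- or hyperglycaemia it says "it will be handled in a standard fashion as outlined in Section 9.5, Procedures for Managing Hypoglycemia and Hyperglycemia".
- Section 9.5, first paragraph: "If a subject develops hypoglycemia during the study period per definitions stated in Appendix 4, the doses of antidiabetic agents will be adjusted". The stated target is a fasting plasma glucose of 70 to 130 mg/dl.

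On contact, 9.5 has subjects record glucose twice daily "and be seen by the Investigator at each visit". Its second paragraph adds: "If during this time a subject experiences hypoglycemia more than twice, he/she must consult with the Investigator". If no reason is found, insulin is cut by 4 units or 10%, or the oral agent is reduced stepwise. The paragraph closes with "These interventions will be subject-specific and must be undertaken under the direction of the Investigator and/or their own health provider". The third paragraph begins "If a subject experiences serious hypoglycemia on a frequent basis, the Investigator may direct the subject to discontinue" and covers all antidiabetic drugs; the study drug may be stopped as well.

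Appendix 4 defines Severe hypoglycaemia as an event needing another person's active help, or a measured glucose below 40 mg/dl. Section 9.5 attaches no separate action to that category.

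**The concern.** There are two separate problems.

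The first is the dose rule. Section 5.9 deals with treatment compliance, and read alone it forbids what 9.5 instructs. A site that lowers insulin after hypoglycaemia has followed 9.5 and departed from 5.9.

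The second is severity. The mandatory consultation counts episodes and does not grade them. Section 5.8 names hypoglycaemia in combination with other antidiabetic drugs as the interaction risk, and inclusion criterion 3 admits subjects on insulin. A subject who needed someone else's help once has no stated instruction to tell the Investigator before the next visit. If the event is also a serious adverse event, the 24-hour reporting time in 9.4 runs from the Investigator's awareness, so it can wait for the same contact.

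**Working it through.** The plan gives no figure on this point, so the check is a comparison of texts plus two small calculations.

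**Step 1: the dose rule.** Section 5.9 says no change and names no exception. Sections 5.8 and 9.5 say to reduce or adjust. Section 5.8 points to 9.5, but 5.9 points to neither. Any reduction made under 9.5 is outside the wording of 5.9.

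**Step 2: what 9.5 attaches to each situation.**

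| Situation | Dose action | Duty to contact the Investigator | Time for that contact |
|---|---|---|---|
| One event, any Appendix 4 type | Adjust toward 70–130 mg/dl | None beyond scheduled visits | None |
| One Severe event | Same as above | None beyond scheduled visits | None |
| Third event | Seek a reason; if none, reduce insulin or oral agent | Subject must consult | None stated; after an insulin cut, observe 3 days, then report |
| Serious and frequent events | Investigator may stop all antidiabetic drugs and the study drug | None added | None |

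The first two rows are the same: severity changes nothing until events become frequent.

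**Step 3: whether other text supplies the missing route.**

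- The American Diabetes Association standard in 9.5 binds the Investigator, who must first know of the event.
- The direction clause in 9.5 can be met by the subject's own provider alone.
- The Appendix 2 diary has a general line on contacting the site with questions or problems, but no hypoglycaemia trigger.
- Section 6.4 allows unscheduled visits at the Investigator's discretion, which again assumes awareness.
- By contrast, the hyperglycaemia paragraph of 9.5 has numeric glucose triggers, a 2-week limit, and referral with termination.

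None of these tells the subject to report one Severe event.

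**Step 4: longest wait to the next visit.** The inputs are the 2-week interval and the ±3-day window, counted from the previous visit (Sections 6.2.2 to 6.2.4).

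- On schedule: 14 days.
- At the window limit: 14 + 3 = 17 days.

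**Step 5: the diary threshold in both units.** The diary lets the subject record in mg/dl or mmol/L. With a molar mass of 180.16 for glucose:

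- 40 mg/dl = 400 mg/L, and 400 / 180.16 = 2.22 mmol/L.
- A reading of 2.2 mmol/L = 2.2 × 180.16 / 10 = 39.6 mg/dl, which is below 40 and so meets the Severe definition.

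A diary trigger must therefore include 2.2 mmol/L itself.

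**The case against.** The best reply is that a sensible reader would reconcile the text. Section 5.9 says should, not must. Section 5.8 comes immediately before it and sends hypoglycaemia to 9.5, and a specific safety section normally governs a general rule. This has force: the 5.9 conflict is mainly one of drafting. It still leaves a compliance section that forbids a required act, and one clause removes the doubt.

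The reply on severity is that 9.5 does act on a single event. Its first paragraph adjusts doses after any Appendix 4 event, and the direction clause implies that a clinician is involved. That also stands. A reader might infer that a subject can comply fully with 9.5 and simply remain on the same dose after a Severe event. The documents do not support that, because the first paragraph says otherwise. What is missing is the route and the time by which the event reaches the Investigator.

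A reader might also infer that the first two paragraphs of 9.5 contradict each other, or that the word serious in the third is undefined. Neither needs correcting here. The first paragraph states a glucose target and the second gives steps, and serious can be read through Section 9.3.2. Labelling the second paragraph a minimum procedure could weaken the duty in the first, and replacing serious with Severe would change a threshold.

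Finally, consent pages are not available, and the detailed instructions given with the drug at Visit 2 are not shown. They may contain a reporting instruction. That limits the claim to what 9.5 and the diary state.

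**Conclusion.** The concern holds in two limited parts. First, 5.9 lacks an exception for dose changes that 5.8 and 9.5 call for. Second, 9.5 states no route or time for reporting one Severe event, so the next contact it states may be the next visit, at 14 days on schedule or 17 with the window.

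These intervals are upper limits. They assume that the event falls just after a visit, that no unseen instruction applies, and that nobody acts sooner. The documents give neither an event rate nor the share of subjects on insulin or secretagogues, so the number of subjects affected cannot be stated.

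Two stronger readings should be resisted.

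- A wait of 20 days can be obtained by counting the windows from randomisation, as Section 4.1 might suggest: (14 + 3) + 3 = 20. That is only one reading. Sections 6.2.2 to 6.2.4 count from the previous visit, and the 18 capsules dispensed under 5.1 cover 17 days but not 20.
- A reader might infer that a reduction under 9.5 removes the subject from the Per Protocol Set. SAP 7.3 leaves the classing of deviations as major or minor to a discussion before database lock, so this is possible but not stated.

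This should be corrected because it concerns subject safety and is cheap. It does not undermine the primary analysis.

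**What to change.** 1. Section 5.9, last sentence: add *except for changes made under Section 9.5*.
2. Section 9.5: after any single event meeting the Appendix 4 definition of Severe, require same-day contact with the Investigator and a review of background diabetes doses at that contact. Leave the first paragraph's duty to adjust doses as it is.
3. Appendix 2 diary instructions: add *Call the site the same day if another person had to give you sugar, glucagon or other help for low blood sugar, or if a reading was below 40 mg/dl (2.2 mmol/L or lower).*

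The cost is wording in three places, a memo to sites, and a few more calls. Same-day contact is a new standard that the documents do not contain; it is proposed here on safety grounds. No endpoint, sample size or visit changes.
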